8.6. Visit 6: Out-patient Follow-up (Day 8±2)

- Obtain vital signs (blood pressure, heart rate, respiratory rate, and oral temperature)
- Review and update concomitant medications

- Perform symptom directed PE
- Obtain blood samples for the following:
 - Clinical Safety Labs
 - PK measurement
 - Serum sample to store for future use (if subject gave consent)
- Counsel both men and women of child-bearing potential on the avoidance of pregnancy
- Counsel all subjects on prevention of COVID-19
- Assessment of Aes and SAEs

8.7. Visit 7: Out-patient Follow-up (Day 15±2)

- Obtain vital signs (blood pressure, heart rate, respiratory rate, and oral temperature)
- Review and update concomitant medications
- Perform symptom directed PE
- Obtain blood samples for the following:
 - Clinical Safety Labs
 - PK measurement
 - ADA
 - MN
- Assessment of Aes and SAEs
- Counsel all subjects on prevention of COVID-19
- Counsel both men and women of child-bearing potential on the avoidance of pregnancy

8.8. Visit 8: Out-patient Follow-up (Day 30 ± 2)

- Obtain vital signs (blood pressure, heart rate, respiratory rate, and oral temperature)
- Review and update concomitant medications
- Perform symptom directed PE
- Obtain blood samples for the following:
 - Clinical Safety Labs
 - PK measurement

- ADA
- MN
- Serum sample to store for future use (if subject gave consent)
- Assessment of Aes and SAEs
- Counsel all subjects on prevention of COVID-19
- Counsel both men and women of child-bearing potential on the avoidance of pregnancy

8.9. Visit 9: Out-patient Follow-up (Day 45± 3)

- Obtain vital signs (blood pressure, heart rate, respiratory rate, and oral temperature)
- Review and update concomitant medications
- Perform symptom directed PE
- Obtain blood samples for the following:
 - PK measurement
 - ADA
- Perform urine pregnancy test on women of child-bearing potential
- Assessment of Aes and SAEs
- Counsel all subjects on prevention of COVID-19
- Counsel both men and women of child-bearing potential on the avoidance of pregnancy

8.10. Visit 10: Out-patient Follow-up (Day 60 ± 3)

- Obtain vital signs (blood pressure, heart rate, respiratory rate, and oral temperature)
- Review and update concomitant medications
- Perform symptom directed PE
- Obtain blood samples for the following:
 - PK measurement
 - ADA
 - MN
- Assessment of Aes and SAEs
- Counsel all subjects on prevention of COVID-19

• Counsel both men and women of child-bearing potential on the avoidance of pregnancy

8.11. Visit 11: Out-patient Follow-up (Day 90±3)

- Obtain vital signs (blood pressure, heart rate, respiratory rate, and oral temperature)
- Review and update concomitant medications
- Perform symptom directed PE
- Obtain blood samples for the following:
 - Clinical Safety labs
 - PK measurement
 - ADA
 - MN
- Assessment of Aes and SAEs
- Counsel all subjects on prevention of COVID-19
- Counsel both men and women of child-bearing potential on the avoidance of pregnancy

8.12. Visit 12: Out-patient Follow-Up (Day 120±5)

- Obtain vital signs (blood pressure, heart rate, respiratory rate, and oral temperature)
- Review and update concomitant medications
- Perform symptom directed PE
- Obtain blood samples for the following:
 - PK measurement
 - ADA
 - MN
- Obtain urine sample for dipstick analysis
- Perform urine pregnancy test on women of child-bearing potential
- Assessment of Aes and SAEs
- Counsel all subjects on prevention of COVID-19
- Counsel both men and women of child-bearing potential on the avoidance of pregnancy

8.13. Visit 13: Out-patient Follow-Up (Day 150±5)

- Obtain vital signs (blood pressure, heart rate, respiratory rate, and oral temperature)
- Review and update concomitant medications
- Perform symptom directed PE
- Obtain blood samples for the following:
 - PK measurement
 - ADA
 - MN
- Obtain urine sample for dipstick analysis
- Perform urine pregnancy test on women of child-bearing potential
- Assessment of Aes and SAEs
- Counsel all subjects on prevention of COVID-19
- Counsel both men and women of child-bearing potential on the avoidance of pregnancy

8.14. Visit 14: Out-patient Follow-Up (Day 180±5)

- Obtain vital signs (blood pressure, heart rate, respiratory rate, and oral temperature)
- Review and update concomitant medications
- Perform symptom directed PE
- Obtain blood samples for the following:
 - Clinical Safety labs
 - PK measurement
 - ADA
 - MN
- Obtain urine sample for dipstick analysis
- Perform urine pregnancy test on women of child-bearing potential
- Assessment of Aes and SAEs
- Counsel all subjects on prevention of COVID-19
- Counsel both men and women of child-bearing potential on the avoidance of pregnancy

8.15. Visit 15: Day 365 ± 5 / Early Termination

- Obtain vital signs (blood pressure, heart rate, respiratory rate, and oral temperature)
- Review and update concomitant medications
- Perform symptom directed PE
- Obtain blood samples for the following:
 - Clinical Safety labs
 - PK measurement
 - ADA
- Obtain urine sample for dipstick analysis
- Perform urine pregnancy test on women of child-bearing potential
- Assessment of Aes and SAEs
- Counsel all subjects on prevention of COVID-19
- Counsel both men and women of child-bearing potential on the avoidance of pregnancy (for subjects who withdraw from the study early)

8.16. Visit 16: Telephone Visit (Day 450 ±5) for Cohorts 1-4

- Review and update concomitant medications
- Assessment of Aes and SAEs
- Counsel all subjects on the prevention of COVID-19
- Counsel both men and women of child-bearing potential on the avoidance of pregnancy

8.17. Visit 17: Telephone Visit (Day 540 ±5) for Cohorts 1-4

- Review and update concomitant medications
- Assessment of Aes and SAEs
- Counsel all subjects on the prevention of COVID-19

8.18. Unscheduled Visit

A subject may return to the clinic for an unscheduled visit at any time. The following activities at a minimum should be performed:

- Obtain vital signs (blood pressure, heart rate, respiratory rate, and oral temperature)
- Perform symptom directed PE as appropriate

- Review and update concomitant medications
- Assessment of Aes and SAEs

9. ASSESSMENT OF SAFETY

Regulatory requirements including the FDA regulations and ICH Guidelines for GCP set forth safety monitoring and reporting responsibilities of sponsors and investigators to ensure the safety and protection of human subjects participating in clinical trials.

Responsibilities

Investigators participating in this clinical trial are responsible for and will:

- evaluate subject safety including assessment of Aes for seriousness, severity, and causality;
- notify the sponsor (RGS) of SAEs immediately;
- provide detailed written reports, including necessary documentation requested by the sponsor or IRB/Independent Ethics Committee (IEC), promptly following immediate initial reports, and;
- inform the IRB/IEC of Aes as required by applicable regulatory requirements.
- have emergency staff and medications such as epinephrine, corticosteroids, bronchodilators, and emergency tool kits for emergent intubation and initial acute cardiopulmonary resuscitative care are available at all clinical sites in the event they are needed during and immediately after IM injections.

9.1. Specification of Safety Parameters

Definitions

Adverse events

ICH E6(R2) defines an AE as any untoward medical occurrence in a patient or clinical investigation subject administered a pharmaceutical product and which does not necessarily have a causal relationship with this treatment. An AE can therefore be any unfavorable and unintended sign (including an abnormal laboratory finding), symptom, or disease temporally associated with the use of medicinal (investigational) product, whether or not related to the medicinal (investigational) product.

FDA defines an AE as any untoward medical occurrence associated with the use of a drug in humans, whether or not considered drug related.

Serious Adverse Events

An SAE is any untoward medical occurrence that at any dose:

• Results in death,

- Is life-threatening*,
- Requires inpatient hospitalization or prolongation of existing hospitalization,
- Congenital anomaly/birth defect;
- Persistent or significant incapacity or substantial disruption of the ability to conduct normal life functions
- Important Medical Event

*Life-threatening adverse event. An adverse event is considered "life-threatening" if, in the view of either the investigator or sponsor, its occurrence places the patient or subject at immediate risk of death. It does not include an adverse event, had it occurred in a more severe form, that might have caused death.

Unexpected

An adverse reaction, the nature or severity of which is not consistent with the applicable product information (e.g. Investigator's Brochure for an unapproved investigational product or package insert/summary of product characteristics for an approved product).

9.2. Methods and Timing for Assessing, Recording, and Analyzing Safety Parameters

9.2.1. Adverse Events

Adverse events will be collected at Day 1 during and after dosing. Any medical condition that is present at the time that the subject is screened should be considered as baseline and not reported as an AE. However, if the condition increases in severity or frequency at any time during the study, it should be recorded as an AE.

All Aes must be graded for severity and relationship to study product based on the Investigator's assessment.

Severity of adverse events will be graded using CTCAE v5.0 (Appendix B).

9.2.2. Relationship to Study Product

Aes and SAEs must be assessed by the investigator to determine relationship to study product. All Aes must have their relationship to study product assessed using the following terms. In a clinical trial the study product must always be suspect.

- **Definitely Related:** There is a definite probability that the study product caused the adverse event.
- **Possibly Related:** There is a reasonable possibility that the study product caused the adverse event. Reasonable possibility means that there is evidence to suggest a causal relationship between the study product and the adverse event

• **Not Related**: There is not a reasonable possibility that the administration of the study product caused the event

To help assess, the following factors may be considered:

- Temporal relationship of the event to the administration of study product;
- Whether an alternative etiology has been identified;
- Biological plausibility;
- Existing therapy and/or concomitant medications.

9.3. **Reporting Procedures**

9.3.1. Adverse Events:

Aes not meeting the criteria for "SAEs," will be captured on the appropriate case report form. Information to be collected for Aes includes event description, date of onset, investigator assessment of severity, relationship to study product, date of resolution of the event, seriousness, and outcome.

All Aes will be followed until resolved or considered stable by the investigator.

9.3.2. Serious Adverse Events

The following procedures will apply to all serious adverse events:

- The Principal Investigator will report any SAE to ICON PVSS within 24 hours of awareness.
- ICON PVSS will perform an initial check of the SAE and contact the site for any missing elements and then inform the ICON MM, and the ISM of the SAE.
- ICON PVSS will record the information on the appropriate serious adverse event report form and send to RGS
- Each SAE will be reviewed and followed to resolution or stability by a study physician
- SAEs will be collected on each subject up to 60 days after his/her last study visit.

Any AE that meets a protocol-defined serious criterion must be submitted immediately (within 24 hours of site awareness) on an SAE form to RGS at the following address:

ICON PVSS

ICON plc PVSS

[name] SAE Email Address: [name] [contact] SAE Fax Number (in case email is not available): [contact]

ICON PVSS will send AE/SAE information to Resilience Government Services, Inc.

Resilience Government ServicesResilience Government Services, Inc.13200 NW Nano CourtAlachua, FL 32615, USASAE [contact]SAE [contact]SAE Email Address: [contact]</t/>

Other supporting documentation of the event may be requested by RGS and should be provided as soon as possible.

ICON plc PVSS will send SAEs with the ICON Drug Safety Physician assessment of causality, expectedness, and any impact on the benefit-risk ratio of the IMP to RGS. The DOD will be notified of the SAE by RGS.

If the investigator becomes aware of an SAE that is suspected to be related to study product up to 60 days after the subject completes the study, the investigator will report the event to ICON PVSS.

9.3.3. Regulatory Reporting

Following notification from the investigator, RGS, the IND sponsor, will report any suspected adverse reaction that is both serious and unexpected to the FDA. RGS will report an adverse event as a suspected adverse reaction only if there is evidence to suggest a causal relationship between the drug and the AE. RGS will notify FDA and all participating investigators (i.e., all investigators to whom the sponsor is providing drug under its INDs or under any investigator's IND) in an IND safety report of potential serious risks from clinical trials or any other source, as soon as possible, but in no case later than 15 calendar days after the sponsor determines that the information qualifies for reporting as specified in 21 CFR Part 312.32. RGS will also notify FDA of any unexpected fatal or life-threatening suspected adverse reaction as soon as possible but in no case later the sponsor's initial receipt of the information. Relevant follow up information to an IND safety report will be submitted as soon as the information is available. Upon request from FDA, RGS will submit to FDA any additional data or information that the agency deems necessary, as soon as possible, but in no case later than 15 calendar days after receiving the request.

All SAEs designated as "not related" to study product(s), will be reported to the FDA at least annually in a summary format.

9.3.4. Reporting of Pregnancy

Pregnancies that occur during the study period will be reported to the Sponsor on the Pregnancy Report form within five days of site awareness.

Efforts will be made to follow all pregnancies occurring prior to 56 days post product administration through to outcome, as described in the Safety Management Plan (e.g. delivery, spontaneous abortion or therapeutic abortion).

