2.1.3. ADM03820 Development

ADM03820 drug product is being investigated for the treatment and prevention of COVID-19 in adults. ADM03820 is a 1:1 mixture of two human IgG1 non-competitive binding anti-SARS-CoV-2 antibodies, mAb2130 (YTE+LALA) and mAb2381 (YTE+LALA), individually expressed in a Chinese hamster ovary (CHO) cell line. Several amino acid changes in the Fc region have been incorporated into mAb2130 (YTE+LALA) and mAb2381 (YTE+LALA) to silence or reduce the effector function of antibodies. The LALA variant eliminates complement binding and fixation as well as Fc- γ dependent antibody-dependent cell-mediated cytotoxicity (ADCC) in both murine IgG2a and human IgG1¹⁶. The YTE mutation was also incorporated to extend circulating half-life of the antibodies¹⁷. RGS worked with Vanderbilt University Medical Center (VUMC), Just-Evotec, ATUM, and Seromyx to develop the ADM03820 anti-SARS-CoV-2 mAbs.

A GLP repeat dose toxicity study was performed to evaluate the safety of ADM03820 in rats when administered by intramuscular injection or intravenous infusion once weekly for three weeks and to evaluate toxicity and reversibility of effects after a 72-day recovery period.

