5.1. Subject Inclusion Criteria

All must be answered yes for the subject to be eligible for study participation

- 1. Informed consent understood and signed
- 2. Healthy male or healthy, non-pregnant, non-lactating female
- 3. Willingness to comply and be available for all protocol procedures for the duration of the study
- 4. Between 18 and 55 years of age on the day of dosing
- 5. Body Mass Index (BMI) of ≥ 18.5 and $\leq 35 \text{ kg/m}^2$
- 6. Female subjects of childbearing potential must have a negative serum pregnancy test at screening and negative urine test on Day 1 prior to dosing
 - Note: A woman is considered of childbearing potential unless post-menopausal (≥ 1 year without menses or without other known or suspected cause and appropriately elevated FSH) or surgically sterilized via bilateral oophorectomy or hysterectomy
- 7. Females of childbearing potential and males agree to use acceptable contraception for the duration of the study.
 - Note: These include progestin implants, intrauterine devices (IUDs), surgical (hysterectomy or tubal ligation; vasectomy) or abstinence. Use of methods such as progestin injectables, combined oral hormonal contraceptives, condoms, and diaphragms will not be acceptable when used alone, but they could be considered, if used in combination with another method (for example, a female using combined oral contraceptives if her male partner is sterile, or if she and her non-sterile male partner use a double-barrier method), after consultation with the RGS ML. All males will be required to use a barrier method (condoms) for the duration of the study
- 8. Screening laboratory tests are within normal ranges or outside the normal ranges and considered not clinically significant by the Principal Investigator
 - If urinalysis by dipstick is abnormal, a complete urinalysis with microscopic evaluation will be performed and the results will supersede the results of the dipstick for blood, glucose, and protein.
 - Menstruating females failing inclusion criteria due to positive blood on urine test may be retested following cessation of menses.
 - Other laboratory values that are outside the range of eligibility but are thought to be due to an acute condition or collection or laboratory error may be repeated once.
- 9. The urine drug screen is negative

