7.5.1.2. Drug Screen

A urine toxicology screen will be performed to detect for the presence of the following: cocaine (and metabolite), barbiturates, benzodiazepines, opiates, THC, methamphetamine/amphetamine, methadone and PCP. The results must be negative for eligibility into the study. A breathalyzer test or blood/saliva alcohol test will also be performed, and results must be negative for eligibility into the study.

7.5.1.3. **Pregnancy Testing**

For women of child-bearing potential, a serum pregnancy test will be done at screening and must be negative. A urine pregnancy test will be done at Visit 2 (Day 1), which must be reported as negative before dosing. A urine pregnancy test will be repeated on Day 4, Day 45, Day 120, 150, Day 180, and 365.

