7.6. Special Assays or Procedures

7.6.1. Pharmacokinetic Assay

Six-mL of blood will be drawn for the analysis of levels of monoclonal antibodies in serum using a validated ELISA. For each timepoint, aliquot at least 0.50 mL each of serum into three 1.8 mL sterile cryogenic vials, freeze and store serum samples at \leq -70°C until shipment.

PK samples will be tested by ELISA at pre-dose, 2, 4, 8, and 24 hours post dose and on Days 3, 4, 8, 15, 30, 45, 60, 90, 120, 150, 180, and 365.

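### The protocol requires reporting of every pregnancy in the study period but plans follow-up to outcome only for those before 56 days post dose, so later outcomes are captured passively and incompletely

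*Protocol*

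**What the plan says.** Protocol section 9.3.4 contains two rules with different windows. On reporting: "Pregnancies that occur during the study period will be reported to the Sponsor on the Pregnancy Report form within five days of site awareness". On outcome: "Efforts will be made to follow all pregnancies occurring prior to 56 days post product administration through to outcome", with the manner of follow-up left to another document ("as described in the Safety Management Plan"). The section does not explain the 56 days, and it does not say whether a pregnancy occurs at conception or at detection.

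Other parts of the protocol use longer windows:

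- Section 5.1, inclusion criterion 7: "Females of childbearing potential and males agree to use acceptable contraception for the duration of the study". Under section 4 that means Day 540 in Cohorts 1-4 and Day 365 in Cohort 5.
- Section 7.5.1.3, on pregnancy testing: "A urine pregnancy test will be repeated on Day 4, Day 45, Day 120, 150, Day 180, and 365".
- Section 7.6.1: after the first-day samples, PK is measured "on Days 3, 4, 8, 15, 30, 45, 60, 90, 120, 150, 180, and 365".
- Section 2.1.3: "The YTE mutation was also incorporated to extend circulating half-life of the antibodies".
- Section 9.1 lists "Congenital anomaly/birth defect" among the SAE criteria. Section 9.3.2 collects SAEs to 60 days after the subject's last visit. SAEs are a primary endpoint (section 3.2.1).

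The SAP contains no analysis of pregnancy outcomes.

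**The concern.** The protocol's contraception, testing and sampling rules treat pregnancy as something to prevent and detect for a year or more after a single dose. The outcome rule stops at 56 days. A pregnancy identified at the Day 150 test, for example, goes onto a report form, and the protocol then makes no commitment to learn how it ended.

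This matters because birth defect is one of the trial's own SAE criteria. Pregnant women are excluded (section 14.4), so incidental pregnancies are the only source of pregnancy-exposure data within this study. The product is first-in-human and designed to circulate longer than an unmodified antibody, so exposure beyond 56 days is plausible, although its level is not documented.

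**Working it through.** The plan gives no figure to reproduce on this point. The check is calendar arithmetic on the stated windows.

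**Inputs**

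| Rule | Protocol section | Cohorts 1-4 | Cohort 5 |
|---|---|---|---|
| Outcome follow-up | 9.3.4 | before 56 days | before 56 days |
| Pregnancy reporting | 9.3.4 | study period (Day 540) | study period (Day 365) |
| Contraception | 5.1 | Day 540 | Day 365 |
| Last urine pregnancy test | 7.5.1.3 | Day 365 | Day 365 |
| Last PK sample | 7.6.1 | Day 365 | Day 365 |
| SAE collection (last visit + 60 days) | 9.3.2 | 540 + 60 = Day 600 | 365 + 60 = Day 425 |

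**1. Length of the gap.** Days with no planned outcome follow-up = last study day − 55, counting from Day 56.
- Cohorts 1-4: 540 − 55 = 485; 485/540 = 90%.
- Cohort 5: 365 − 55 = 310; 310/365 = 85%.

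Counting from Day 57 gives 484 and 309 days, and the same percentages. These are shares of calendar days, not of pregnancies or exposure.

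**2. Tests after the cut-off.** The post-dose tests are on Days 4, 45, 120, 150, 180 and 365. Four of the six (Days 120, 150, 180, 365) come after Day 56. No test is scheduled between Days 45 and 120, so a pregnancy first detected at Day 120 could have begun on either side of the cut-off.

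**3. What SAE collection can reach.** Assume 259-280 days from conception to delivery; the documents give no figure. Latest conception delivering inside the window = window end − interval.
- Cohorts 1-4: 600 − 280 = Day 320; 600 − 259 = Day 341.
- Cohort 5: 425 − 280 = Day 145; 425 − 259 = Day 166.

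This holds for subjects who complete the study. For those who leave early the last visit is earlier, and so is the end of the window.

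**4. Residual product.** No half-life is given, so the values below are assumptions. With first-order decline and absorption ignored, fraction remaining = 0.5^(days/half-life).

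| Assumed half-life | Day 56 | Day 180 |
|---|---|---|
| 21 days | 16% | 0.3% |
| 60 days | 52% | 12.5% |
| 90 days | 65% | 25% |

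Across this range a substantial fraction could remain at Day 56. Whether much remains by Day 180 depends almost entirely on the half-life.

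**The case against.** The strongest reply is that later pregnancies are not lost. Reporting under 9.3.4 has no 56-day limit, and testing continues to Day 365. A birth defect is an SAE, SAEs are followed to resolution or stability (9.3.2), and AE and SAE review takes place at every contact, to Day 540 in Cohorts 1-4. With the same assumed interval, conceptions up to about Day 260-281 (540 − 280 to 540 − 259) in those cohorts deliver while scheduled review is still running. All of this stands. A reader might infer from the 56-day limit that later pregnancies and any birth defects go unascertained; the documents do not support that. However, capture depends on the site learning of the birth, and it ends before term for the later conceptions in step 3.

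A second reply is that 9.3.4 does not forbid following later pregnancies and that the Safety Management Plan may extend follow-up. That plan was not available, so this cannot be excluded. But the sentence cites it for how follow-up is done, while the 56-day limit is set in the protocol itself.

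Third, the 90% and 85% figures might be read as the share of safety information lost. They are not: late in follow-up there may be little product left, and 10 of the 50 subjects receive placebo.

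Finally, 56 days does appear elsewhere, as the blood or plasma donation window before enrolment (exclusion criterion 11). That window serves another purpose and does not explain the limit here.

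**Conclusion.** The point holds in a limited form. For pregnancies from 56 days post dose onward the protocol commits to reporting but not to follow-up to outcome, and it gives no reason for the difference. The uncommitted period is 485 of 540 days in Cohorts 1-4 and 310 of 365 days in Cohort 5. SAE collection covers part of it passively, and closes before term for conceptions after about Day 320-341 or Day 145-166 respectively, given the assumed 259-280 days to delivery.

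How much exposure these later pregnancies would carry is unknown from the documents; the residual fractions are illustrations under assumed half-lives. Nor do the documents show that these pregnancies would be the only reproductive information on the product, since material outside the protocol and SAP was not seen. Few pregnancies are expected among 50 subjects using contraception. This is a cheap improvement to safety data collection and does not threaten the trial's main conclusions.

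**What to change.** In section 9.3.4, make the outcome follow-up window the same as the reporting window already stated there, namely pregnancies occurring during the study period, and align the Safety Management Plan. This also removes the need to date a pregnancy relative to 56 days. If the sponsor prefers to keep the limit, the protocol should justify it against the contraception, pregnancy-testing and PK windows and say whether occurring means conception or detection.

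The cost is one sentence in the protocol, a matching edit to the Safety Management Plan, and a few outcome contacts, some of them after the subject's last visit. No dosing, contraception or visit rule changes.
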